# Statistical Design

Under these hypotheses, a two-stage group sequential design using alpha and beta spending function approach with Lan DeMets spending function (O'Brien-Fleming efficacy boundaries and non-binding Pocock futility boundaries) will be used leading to a maximum sample size of 30 evaluable patients and an interim analysis based on 15 evaluable patients (implemented in EAST® 6.3) with a test proportion with normal approximation to the binomial distribution.

#### 7.2 ISC for Phase I

ISC will review safety data when 6 evaluable patients for Phase I have reached their Day 29 visit:

- In case no more than 1 Dose-Limiting Toxicity (DLT) is observed in 6 patients and no occurrence of any landmark AE (see section 2.1), then accrual in the Phase IIa part of the study will start at the same dose level.
- In case of more than one DLT is observed, or the occurrence of a landmark AE, one deescalation regimen is planned to Level -1, depending on the DLT profile relative to the known toxicity of each component of the combination, as judged by the ISC:
  - o 3 bi-weekly IT injections of 3x10^8 pfu for Pexa-Vec and 240 mg q2 weeks for nivolumab OR
  - o 3 bi-weekly IT injections of 10^9 pfu for Pexa-Vec and 240 mg q3 weeks for nivolumab.

## 7.3 Interim analysis for Phase II

## 7.3.1 Purpose of Interim Analyses

When 50% of evaluable targeted number of patients have reached their W12 visit or discontinued the study treatment due to disease progression, an interim analysis will be conducted to either stop the trial for futility (and not expose more patients to the combination), or stop the trial for efficacy or continue the trial as planned.

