#### Nivolumab

Nivolumab is a programmed death receptor-1 (PD-1) blocking antibody. It will be supplied in 40 and/or 100 mg vials (10 mg/mL).

Patients will be administered as an IV infusion over 60 minutes every 2 weeks, with the targeted dose of 240 mg.

Accounting for the immunotherapeutic effect of both drugs and for the peculiar kinetics of clinical efficacy of these treatments, guidance is provided to continue treatment beyond evidence of radiologic progression.

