# 9.1.1 Imaging Data Acquisition

All patients will undergo CT (preferred) or MRI (if CT not possible) at Screening (up to 28 days before Day 1). Tumors will be numbered with a unique number and identified as Target or Non-Target tumors (refer to the next paragraph for definitions). Tumors should be assigned the next available chronological number wherever possible.

Collection of radiographic imaging scans will then occur at Week 6 ( $\pm 2$  days) and continue thereafter every 6 weeks ( $\pm 4$  days).

Beyond 12 months of treatment, the evaluations will be performed every 12 weeks.

If a patient discontinues the treatment phase prior to documented radiographic progression (e.g. permanently stops taking the study medication), PFS Follow-up Visits will be performed every 6 weeks for radiology evaluation until confirmed radiographic progression or until premature study discontinuation.

Specific imaging acquisition instructions are provided in the Imaging Manual provided by the core imaging laboratory.

Preferred Modality: Triphasic helical/spiral CT of the abdomen (pre-contrast, arterial phase, and portal venous phase; delayed imaging of the abdomen is optional) and post-contrast helical/spiral CT of the chest and pelvis. All follow-up scans must also be CT. If a CT IV contrast allergy (toxicity) develops after the patient has been randomized, then a DCE MRI of the abdomen and pelvis with gadolinium contrast will be required along with a non-contrast CT of the chest.

Alternative Modality: While triphasic CT remains the preferred modality for the abdomen, if a patient is unable to undergo triphasic CT due to iodinated contrast allergy, then Dynamic Contrast Enhanced Magnetic Resonance Imaging (DCE MRI) of the abdomen and pelvis with gadolinium contrast will be required along with a non-contrast CT of the chest. The abdominal MRI will be triphasic in nature, and the pelvic MRI will be performed following MRI of the abdomen. If an MRI is performed at screening, all follow-up scans must also be DCE MRI of the abdomen and pelvis with gadolinium contrast with a non-contrast CT of the chest.

The same method of assessment and the same technique should be used to assess each identified and reported lesion for the radiological baseline (screening CT/MRI) and each follow up scan collected during the study.

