#### 7 STATISTICAL DESIGN

## 7.1 Sample size determination for Phase IIa part

## Hypotheses

As the patient survival benefit may be correlated with either radiological response of tumors or/and prolonged stabilization of the disease, the analysis of efficacy will consider ORR as primary endpoint. Sample size justification will use available data on ORR, as such: in a Phase I/II trial, 8/42 (19%) patients with previously treated HCC experienced an objective response when treated with single-agent nivolumab (El-Khoueiry et al., ASCO 2015). Therefore, a response rate of 15%-20% with the combination of Pexa-Vec + nivolumab in not previously treated HCC patients would be considered disappointing, while a response rate of 35% or more would be promising and would encourage further study of the regimen in these patients. The null hypothesis for response rate H0 is set at 15%, the alternate hypothesis of efficacy is set at H1=35%, the type I error  $\alpha$  is set at 5% one sided and the power is set at 80%.

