## 7.3.3 Stopping Rules

If there are 3 or fewer responses in these 15 patients (20% of responders or less), the study could be stopped for futility. If there are 6 or more responses in these 15 patients (40% of responders or more), the null hypothesis will be rejected and the combination will be considered to have a substantial activity to be of further interest and the study could be stopped for efficacy. Otherwise 15 additional evaluable patients will be accrued for a total of 30.

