## 8.7.1 Primary efficacy endpoint and analysis

For Phase IIa part the primary endpoint is the Overall response rate (ORR) which is the proportion of patients, whose best overall response is either CR or PR, confirmed at least 4 weeks after initial documentation. A test proportion with normal approximation to the binomial distribution will be used and null hypothesis will be rejected if 8 or more responses are observed in the 30 evaluable patients (26.7% of responders or more)

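### The interim opens at Week 12, before the latest of the 15 patients can have a Week 12 response confirmed, and the SAP does not say which responses count against the 3/15 and 6/15 boundaries

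*SAP*

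**What the plan says.** - **Trigger.** SAP 7.3.1 opens the interim "When 50% of evaluable targeted number of patients have reached their W12 visit or discontinued the study treatment due to disease progression". SAP 7.3.2 sets the number at 15 evaluable patients and lets comparable Phase I patients count among them. Protocol 12.7 gives the number but no timing.
- **Endpoint.** SAP 8.7.1 defines ORR as the proportion of patients "whose best overall response is either CR or PR, confirmed at least 4 weeks after initial documentation". Protocol 8.1 and 12.3.3 give the same definition. No unconfirmed version appears.
- **Scans.** Protocol 9.1.1: "Collection of radiographic imaging scans will then occur at Week 6", then every 6 weeks.
- **Rule.** SAP 7.3.3: "If there are 3 or fewer responses in these 15 patients (20% of responders or less), the study could be stopped for futility". Six or more responses reject the null hypothesis and permit a stop for efficacy. The section does not say whether a response must be confirmed, or what happens to one awaiting its confirmatory scan.
- **Design.** SAP 7.1 sets H0 at 15%, H1 at 35%, one-sided 5% type I error and 80% power, with O'Brien-Fleming efficacy and non-binding Pocock futility boundaries.

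**The concern.** The boundaries were derived for a response variable that is complete in every patient. At the interim it is not complete for patients who have only just reached Week 12: a response first seen at Week 12 normally waits for the Week 18 scan, and later responses are not yet visible.

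If confirmed responses are counted, the error runs one way, towards futility. Week 6 is only about four weeks after the first nivolumab infusion (Day 15) and two weeks after the third Pexa-Vec injection (Day 29). Protocol 1.2.3.3 describes transient tumour swelling after Pexa-Vec, and the synopsis refers to the "peculiar kinetics of clinical efficacy of these treatments". Patients who stop for progression satisfy the trigger early, while responders must wait for Week 12.

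If unconfirmed responses are counted, the Week 12 responders are kept, but 6/15 is then met on an easier endpoint than the one tested.

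At stake is a decision that can end the trial in either direction, on a count whose definition would have to be chosen after the data are visible.

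**Working it through.** **Inputs.** H0 15%, H1 35%, one-sided alpha 5%, power 80%, looks at 15 and 30, boundaries 3/15, 6/15 and 8/30 (SAP 7.1, 7.3.3, 7.4). Scans at Weeks 6, 12, 18 and so on (protocol 9.1.1). Phase I stagger: first patient followed to Day 29, then 2 weeks between patients (protocol 3.1.1). Phase I recruitment complete January 2018, Phase IIa March 2019 (protocol 3.1.3). The share of responses first seen by Week 6 is **not given**; 80% down to 50% is assumed.

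**1. The plan's own boundaries.**
- O'Brien-Fleming spending at half the information: 2[1 − Φ(1.960/√0.5)] = 0.0056, so z = 2.538. Count: 15 × (0.15 + 2.538 × √(0.15 × 0.85/15)) = 5.76, so 6.
- Pocock beta spending: 0.20 × ln(1 + (e − 1) × 0.5) = 0.124, so z = −1.155. Count: 15 × (0.35 − 1.155 × √(0.35 × 0.65/15)) ≈ 3.1, so 3.
- The final boundary comes to 7.75, so 8, and normal-approximation power at 30 patients is 80.6%.

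The stated design reproduces, and it treats all 15 interim outcomes as final.

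**2. Complete data, exact binomial.** P(X ≤ 3 | 15, 0.35) = 0.0016 + 0.0126 + 0.0476 + 0.1110 = 17.3% after rounding. Exact power is 78.3% if the futility rule is obeyed and 87.9% if it is ignored.

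**3. What one patient can contribute.**

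| Response first seen | Confirmed at scheduled scan |
|---|---|
| Week 6 | Week 12 |
| Week 12 | Week 18 (Week 16 at the earliest, with an extra scan) |
| Week 18 | Week 24 |

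**4. Follow-up of the 15 at the trigger.** Planned accrual: 30 − 6 = 24 patients over 14 months, or 24/14 = 1.71 per month. With 30.4375/7 = 4.35 weeks per month, that is one patient every 4.35/1.71 ≈ 2.5 weeks. When the last of the 15 reaches Week 12, the two before are at about Weeks 14.5 and 17.1, and the next is at about Week 19.6. So 3 of the 15 have not reached Week 18.

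**5. Chance of 3 or fewer confirmed responses at a true ORR of 35%.** Each patient's interim response probability is 0.35 times the share of responses confirmable at that patient's follow-up; the count is the sum over the 15. Assumed shares first seen at Weeks 6/12/18/24 are 80/15/5/0, 70/20/10/0, 60/25/10/5 and 50/25/15/10. With complete data the figure is 17.3% throughout.

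| Share first seen at Week 6 | 80% | 70% | 60% | 50% |
|---|---|---|---|---|
| Week 12 trigger, planned accrual (3 of 15 below Week 18) | 20.8% | 23.0% | 26.3% | 30.5% |
| Week 12 trigger, twice that accrual (5 below) | 23.6% | 27.9% | 33.1% | 40.3% |
| Fastest Phase I stagger, then 9 patients entering together (10 below) | 29.7% | 38.1% | 48.3% | 60.6% |
| All 15 exactly at Week 12 | 35.8% | 47.9% | 61.0% | 74.0% |
| Planned accrual, interim held until all reach Week 18 | 18.0% | 18.7% | 20.0% | 22.2% |

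The fourth row is the plain binomial P(X ≤ 3 | 15, 0.35f), for example 0.35 × 0.80 = 0.28 giving 35.8%. At planned accrual the expected confirmed ORR at the interim is 33.4% down to 29.6%, not 35%.

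**6. Power.** As a simple check, let three patients sit at Week 12 and twelve be complete. The boundary is crossed with probability 20.3%, 21.8%, 23.5% and 25.2%. Power with the rule obeyed is 75.8%, 74.4%, 73.0% and 71.5%, against 78.3% with complete data.

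**7. The other reading.** The documents give no rate at which first responses fail to confirm, so the loosening of 6/15 under an unconfirmed count cannot be sized.

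**The case against.** A reader might infer that no response after Week 6 can count in any of the 15, and that the rule will therefore stop an active combination far more often than planned, with crossing probabilities of 36% to 61%. The documents do not support that:

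- Week 12 is the minimum follow-up, reached by the last patient to qualify. Up to six of the 15 are earlier Phase I patients entered in sequence, and at planned accrual about twelve will have passed Week 18. The 36% to 61% range needs all 15 to sit exactly at Week 12, with 80% to 60% of responses confirmable.
- The futility bound is non-binding, and SAP 7.3.3 only permits stopping. Those making the decision could see pending responses and continue.
- No time-to-response data are given. The synopsis remark on kinetics supports treating beyond progression and says nothing about when responses appear.
- SAP 7.3.3 does not specify confirmed responses, so an under-count is one of two readings. Nor does SAP 7.7.1 tie the data cut-off to the last Week 12 visit; some further scans may be in hand by then.

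All of this stands, and it limits the size of the problem. It does not remove it. Non-binding futility protects the type I error, but the design spends beta at the interim, so the 80% power assumes the boundary is followed. The instruction to weigh DCR, TTP and survival first is attached to the final rule (SAP 7.4, protocol 12.1 and 12.8) and does not appear in SAP 7.3 or protocol 12.7. Since the only ORR definition is the confirmed one, that is the natural reading.

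**Conclusion.** The point holds in limited form. The stated trigger, scan interval and confirmation rule together leave the interim ORR incomplete for the latest-enrolled patients, and the counting rule is not written down. Under the confirmed reading, at a true ORR of 35%, the chance of crossing 3/15 rises from 17% to about 21% to 31% at planned accrual, and further if enrolment is faster or clustered. The range depends on the assumed timing of first responses and on the protocol's accrual dates; the effect on power depends also on the non-binding rule being followed. Under the unconfirmed reading the risk moves to the 6/15 efficacy stop and cannot be quantified. This should be fixed before the interim; it is a cheap improvement. Confidence is medium: the direction is certain under the confirmed reading, the size is not.

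**What to change.** In SAP 7.3.1 and 7.3.3, with a matching sentence in protocol 12.7:

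1. Hold the interim until each of the 15 has had the Week 18 assessment, or has progressed, died or can no longer have a response confirmed. Patients off treatment without progression who are still being scanned (protocol 8.11) are not released early.
2. For the 6/15 efficacy stop, count confirmed responses only.
3. For futility, do not stop if confirmed plus pending CR/PR exceed 3.
4. If Week 12 is kept, apply the same counting rule there, so that a pending Week 12 response blocks a futility stop.
5. State the data cut-off for the interim.

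At planned accrual, waiting for Week 18 alone brings the crossing probability to 18% to 22%. Week 18 is not full maturity, since a response first seen there is still unconfirmed; item 3 covers that case.

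Cost: wording, and a delay of up to about six weeks. If enrolment continues meanwhile, that is about 6/2.5 ≈ 2 extra patients at planned accrual. Futility stopping becomes slightly more lenient, because some pending responses will not confirm. The non-binding design does not rely on futility stops to hold its nominal type I error.

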## 7.3.2 Planned Schedule of Interim Analyses

At interim analysis, enough patients will be treated to obtain a total of 15 evaluable patients, including comparable patients of the Phase I part (same inclusion/exclusion criteria and same treatment regimen) still evaluable for Phase II part.

## 7.3.3 Stopping Rules

If there are 3 or fewer responses in these 15 patients (20% of responders or less), the study could be stopped for futility. If there are 6 or more responses in these 15 patients (40% of responders or more), the null hypothesis will be rejected and the combination will be considered to have a substantial activity to be of further interest and the study could be stopped for efficacy. Otherwise 15 additional evaluable patients will be accrued for a total of 30.

## 7.4 Final Statistical Analysis

At final analysis, enough patients will be treated to obtain a total of 30 evaluable patients, including comparable patients of the Phase I part (population, treatment regimen) still evaluable for Phase II part.

The null hypothesis will be rejected if 8 or more responses are observed in the 30 evaluable patients (26.7% of responders or more) with a power of 80% and a type I error of 5%. It should nevertheless be reminded that given the mechanism of action of the drugs involved and the effects of immunotherapy on tumor behavior, ORR may not be the best measure of anti-tumor activity. For this reason, consideration will be given to DCR, TTP and survival parameters prior to deciding that the combination does not warrant further exploration.

Drafts TFLs will be produced and reviewed before the database export to ensure that no critical data is missing and to check potential inconsistency in the database.

Follow-up statistical analyses will be conducted when the study will be closed and after the database lock.

# 7.5 Data Review Meeting

A data review meeting will occur:

- Before analysis for Independent Safety Committee at the end of Phase I
- Before Interim Analysis
- Before final statistical analysis

The purpose of data review meeting will be to discuss the following issues:

- Resolve the last issues in data
- Completeness of data capture and coding
- Presence of non-resolved adverse events

- Action to be taken to any of this above data issues
- Classification of protocol deviations into minor and major deviations
- Allocation of subjects to various analysis populations
- Finalize the statistical analysis plan

Data listings will be produced by CRO before the data review meeting, the list of listings to produce will be defined in agreement with Transgene.

## 7.6 Missing data

Measurements that were not performed or not recorded are treated as missing data.

No imputation will be done for missing data, excepted for calculation of duration with missing and incomplete dates for birth and adverse events (AE). Missing data will be noted as missing in appropriate tables/listings.

Imputation Rules for Partial Birthdates:

- If the month and year are present, impute the day by the 15th day of that month.
- If only the year is present, impute by July 1st of that year.

Imputation Rules for Partial or Missing Start Dates for AE:

- If the month and year are present, impute the day by the first day of that month. If the month and year are the same as those of the date of first dose of IMP, impute the day with the day of first treatment administration.
- If only the year is present, impute by January 1st. If the year is the same as the year of the date of first dose of IMP, impute by the date of first treatment administration.
- If the start date is entirely missing, impute by the date of first treatment administration.

Imputation Rules for Partial or Missing Stop Dates for AE:

- If the month and year are present, impute the day by the last day of that month.
- If only the year is present, impute by December 31st of that year.
- If the stop date is entirely missing, assume the event is ongoing.

#### 7.7 Definitions and Derived variables

#### 7.7.1 **Definitions**

Baseline: Unless otherwise specified, baseline is the last measurement taken prior to the first injection of IMP.

## Study day:

For post-study treatment administration measurements, study day will be calculated using the start date of treatment as the origin, i.e. the study day will be calculated as (date of assessment) – (start date of study treatment) +1. Then study day 1 will be the first day of first study treatment administration.

For pre-study treatment administration measurements, the study day will be negative and calculated as (date of assessment) – (start date of study treatment).

Cut-off date: For a given analysis (interim, final and follow-up analysis), data in the database with a date prior to the cut-off date must be clean. The cut-off date will be the latest date considered for cleaning activities for a given lock.

Only data with an assessment date or event start date (e.g., vital sign assessment date or start date of an AE) prior to or on the cut-off date will be included in the statistical analysis. (Example: If cut-off date is 15JUN2016 then an AE starting on 15JUN2016 or before will be reported, whereas an AE with start date on 16JUN2016 will not be reported).

All AE or concomitant medications with start date before or on the cut-off date and end date after the cut-off date will be reported as 'continuing at the cut-off date'. The end data will be considered as missing data and will be displayed as such in listing.

## 7.7.2 Derived variables

The following conventions will be used:

- 1 month corresponds to 365.25/12=30.4375 days.
- 1 year corresponds to 365.25 days.

The following variables will be calculated:

• Age expressed in years: the age at informed consent form (ICF) signature presented in whole years (rounded down to the whole year)

INT([date of ICF signature - date of birth +1]/365.25)

- Body Mass Index (BMI) expressed in kg/m^2: Weight (kg) / Height (m^2)
- Duration of an event expressed in days: End date Start date + 1

The following survival variables will be calculated:

- TTP expressed in months = (Date of first documented radiographic tumor progression date of first treatment administration +1)/30.4375
  - Or (Date of last evaluable tumor assessment date of first treatment administration +1)/ 30.4375 in case of censoring.
- PFS expressed in months = (MIN(Date of first documented radiographic tumor progression, Date of death from any cause) date of first treatment administration +1)/30.4375
  - Or, (Date of last evaluable tumor assessment date of first treatment administration +1)/30.4375 in case of censoring.
- OS expressed in months = (Date of death from any cause date of first treatment administration + 1)/30.4375
  - Or, (Date of last contact date of first treatment administration +1) /30.4375 in case of censoring.
- DoR expressed in months for patients whose best overall response was CR or PR = (MIN(Date of first documented disease progression, date of death from underlying disease)
   Date of first documented response +1)/30.4375
  - Or, (Date of the last evaluable tumor assessment Date of first documented response +1)/30.4375 in case of censoring.

The following variables will be derived for Pexa-Vec and Nivolumab treatment information:

• Duration of IMP exposure: expressed in weeks and calculated as

[(Date of last IMP administration) - (Date of first IMP administration) +1]/7

• Relative Dose Intensity (%): expressed as a percentage and defined as the ratio of "delivered" to the "planned" dose intensity. The dose intensity is the total amount of IMP given a fixed unit of time. A Relative Dose Intensity of 100% indicates that the IMP was administered at the dose planned per protocol, without delay and without cancellations. It is calculated as

100 x IMP Actual Dose Intensity / IMP Planned Dose Intensity

Study IMP parameters definitions for dose level 1 are defined in the following table to derive relative dose intensity.

|                            | Pexa-Vec                                | Nivolumab                      |
|----------------------------|---|--------------------------------|
| Dose schedule per protocol | 109 pfu at D1, D15 and D29              | 240 mg every 2 weeks           |
| Actual Dose                | Actual dose expressed in pfu is defined | Actual dose expressed in mg is |
| * 9                        | as                                      | defined as Total dose (mg); as |

|  | (Total volume injected / Total volume prepared) x Dose Pexa-Vec (pfu); as reported in eCRF page "Pexa-Vec IT injection"                | reported in eCRF page "Nivolumab Administration"  |
|--|--|---|
| Actual Cumulative Dose                     | Actual Cumulative Dose expressed in pfu is defined as the sum of the actual doses  | Actual Cumulative Dose expressed in mg is defined as the sum of the actual doses  |
| Actual Dose Intensity (intensity per week) | Actual Dose Intensity expressed in pfu/wk is defined as Actual Cumulative Dose / [(Last administration - first administration + 14)/7] | Actual Dose Intensity expressed in mg/wk is defined as Actual Cumulative Dose / [(Last administration - first administration + 14)/7] |
| Planned Dose Intensity                     | 5 x 10  pfu/week   | 120 mg/week   |

All laboratory parameters will be expressed in the International System (SI) of units and the intensity grade using CTCAE version 4.03. A grade of 0 will be assigned when the value is within normal limits. In the case a local laboratory normal range overlaps into the higher (i.e., non-zero) CTC grade, the laboratory value will still be taken as within normal limits and assigned a CTC grade of 0. When normal limits are missing and needed for intensity grade determination, the grade will be set at missing. If normal limits are missing but not needed, grade intensity will be calculated as usual with CTCAE ranges.

Laboratory values recorded as "value < x" or "value > x" will be handled as equal to:

- x 0.001 if value recorded as "value < x"
- x + 0.001 if value recorded as "value > x"

for the calculation of descriptive parameters and for the value derived in SI units. Other methods could be investigated for specific parameters. In individual listings they will be presented as "< x" or "> x".

Calculated creatine clearance with Cockroft formula and Corrected Calcium will be also provided in table and listing.

Creatinine Clearance (CRCL) - Cockroft formula:

CRCL(Male) (mL/min) = 1.23 x weight (kg) x (140 - Age)/creatinine(umol/l)

CRCL(Female) (mL/min) = 1.04 x weight (kg) x (140 - Age)/creatinine(umol/l)

Corrected Calcium - Cockroft formula:

Corrected Calcium (mmol/L) = Serum Calcium (mmol/L) + 0.02 \* (40 - albumin [g/L])

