## 8.9 Pexa-Vec injection boost Visits

Additional Pexa-Vec boosts may be performed in patients based on a case by case discussion between the investigator and Transgene, on the grounds of individual patient benefit. In any case, Pexa-Vec boosts will be performed no sooner than Week 12 and will be combined with a nivolumab infusion session. At such visits, patients will complete the following procedures:

- Complete physical examination, including weight, vital signs, and ECOG PS
- Skin and mucosal examination; AEs and concomitant medications reporting
- Blood sample collection for the following testing: hematology, chemistry, coagulation and CRP.
- Pregnancy test (urine) for WOCBP (if positive, an ultrasound will be performed to confirm pregnancy).

Patients will be monitored for troponin T or I blood level 3 and 8 days (± 1) after Pexa-Vec administration.

Patients will undergo an ECG 8 days ( $\pm$  1) after Pexa-Vec administration.

Patients will undergo an ECG 3 days (± 1) after Pexa-Vec administration, in case of troponin clinically significant increase.

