| Lymphocytes   | 10  /L | Investigations                          | Lymphocyte count increased    | 1   | >4x10  /L - 20*10  /L | >20*10  /L            | . ₹   |

Confidential Version 3.0 – 12DEC2018

Page 49/51

| Sodium        | mmol/L     | Metabolism and nutrition disorders | Hyponatremia         | <lln -="" 130="" l<="" mmol="" th="">1	<130 - 120 mmol/L	<120 mmol/L	</lln>                    | 1                 | <130 - 120 mmol/L                  | <120 mmol/L  |
|---------------|------------|------------------------------------|----------------------|--|-------------------|------------------------------------|--------------|
|               |            |                                    |                      |  |                   |                                    |              |
| Lab Test Name | SI
Unit | CTCAE v4.03                        | CTCAE v4.03 Term     | Grade 1  | Grade 2           | Grade 3                            | Grade 4      |
| Sodium        | mmol/L     | Metabolism and nutrition disorders | Hypernatremia        | >ULN - 150 mmol/L  | >150 - 155 mmol/L | >155 - 160 mmol/L                  | >160 mmol/L  |
| Magnesium     | mmol/L     | Metabolism and nutrition disorders | Hypomagnesemia       | >ULN - 1.23 mmol/L   | ı                 | >1.23 - 3.30 mmol/L                | >3.30 mmol/L |
| Magnesium     | mmol/L     | Metabolism and nutrition disorders | Hypermagnesemia      | <lln -="" 0.5="" l<="" mmol="" td=""><0.5 - 0.4 mmol/L	<0.4 - 0.3 mmol/L	<0.3 mmol/L	</lln> | <0.5 - 0.4 mmol/L | <0.4 - 0.3 mmol/L                  | <0.3 mmol/L  |
| Phosphate     | mmol/L     | Metabolism and nutrition disorders | Hypophosphatemia     | <lln -="" 0.8="" l<="" mmol="" td=""><0.8 - 0.6 mmol/L	<0.6 - 0.3 mmol/L	<0.3 mmol/L	</lln> | <0.8 - 0.6 mmol/L | <0.6 - 0.3 mmol/L                  | <0.3 mmol/L  |
| Potassium     | mmol/L     | Metabolism and nutrition disorders | Hypokalemia          | <lln -="" 3.0="" l<="" mmol="" td="">ı	<3.0 - 2.5 mmol/L	<2.5 mmol/L	</lln>                    | ı                 | <3.0 - 2.5 mmol/L                  | <2.5 mmol/L  |
| Potassium     | mmol/L     | Metabolism and nutrition disorders | Hyperkalemia         | >ULN - 5.5 mmol/L  | >5.5 - 6.0 mmol/L | >6.0 - 7.0 mmol/L                  | >7.0 mmol/L  |

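### The SAP's Pexa-Vec relative dose intensity is 100% after one, two or three on-schedule injections, and its magnesium limits are swapped between hypo- and hypermagnesemia; both are errors in descriptive tables only

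*SAP*

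**What the plan says.** **Dose intensity.** SAP 7.7.2 gives the dose level 1 schedule as "109 pfu at D1, D15 and D29" (the exponent is flattened in the published text; the dose is 10^9 pfu). The cumulative dose has no restriction to the planned injections: "Actual Cumulative Dose expressed in pfu is defined as the sum of the actual doses". The actual weekly intensity is "Actual Dose Intensity expressed in pfu/wk is defined as Actual Cumulative Dose / [(Last administration - first administration + 14)/7"], the planned intensity is "5 x 10 8 pfu/week" (5 x 10^8), and RDI is "100 x IMP Actual Dose Intensity / IMP Planned Dose Intensity". The section also fixes what the number should mean: "A Relative Dose Intensity of 100% indicates that the IMP was administered at the dose planned per protocol, without delay and without cancellations". Protocol 8.9 allows further injections case by case: "Pexa-Vec boosts will be performed no sooner than Week 12". SAP 8.6.1 lists RDI among the exposure summaries by cohort.

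**Magnesium.** In SAP Appendix 1 the hypomagnesemia row starts at ">ULN - 1.23 mmol/L" and rises to above 3.30 mmol/L. The hypermagnesemia row starts below the lower limit of normal and falls to below 0.3 mmol/L. SAP 8.8.2 uses this appendix for shift tables, with two tables for any parameter that can be abnormal in both directions.

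**The concern.** Pexa-Vec has a fixed course of three injections, but the RDI denominator follows the injections actually given. When injections are dropped at the end of the course, both the dose and the time shrink, and the ratio stays put. The measure then cannot do what the SAP says it does. In the other direction, a boost adds one dose to the numerator and at least eight extra weeks to the denominator (Day 29 to Day 85), so more virus yields a lower RDI. A clinical study report could print RDI 100% beside a count of cancelled injections, and could rank the most heavily treated patients lowest on that line.

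The magnesium rows contradict the rest of their own table. The shift tables that depend on them would report low values as high and high values as low if a programmer copied the appendix as it stands.

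**Working it through.** **Inputs.** Full-volume injections of 10^9 pfu; planned days 1, 15 and 29; planned intensity 5 x 10^8 pfu/week; denominator (last - first + 14)/7 weeks (all SAP 7.7.2). Protocol 6.3.1 equates Day 29 with week 4, so Week 12 is Day 85, Week 14 is Day 99, Week 18 is Day 127 and Week 24 is Day 169.

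**The SAP's own figure.** Full course: (29 - 1 + 14)/7 = 6 weeks; 3 x 10^9 / 6 = 5 x 10^8 pfu/week. The stated planned intensity reproduces, and RDI = 100%.

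**Other courses under the SAP formula:**

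| Injections given | Weeks in denominator | pfu/week | RDI |
|---|---|---|---|
| D1 | 14/7 = 2 | 10^9/2 = 5.00 x 10^8 | 100% |
| D1, D15 | 28/7 = 4 | 2 x 10^9/4 = 5.00 x 10^8 | 100% |
| D1, D29 (D15 missed) | 42/7 = 6 | 2 x 10^9/6 = 3.33 x 10^8 | 66.7% |
| D1, D15, D36 (third a week late) | 49/7 = 7 | 3 x 10^9/7 = 4.29 x 10^8 | 85.7% |
| Full course + boost D85 | 98/7 = 14 | 4 x 10^9/14 = 2.86 x 10^8 | 57.1% |
| Full course + boost Week 18 | 140/7 = 20 | 4 x 10^9/20 = 2.00 x 10^8 | 40.0% |
| Full course + boost Week 24 | 182/7 = 26 | 4 x 10^9/26 = 1.54 x 10^8 | 30.8% |
| Full course + boosts Weeks 12 and 14 | 112/7 = 16 | 5 x 10^9/16 = 3.13 x 10^8 | 62.5% |

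The formula does register a delay, and it registers a missed middle injection. It does not register missed final injections. Two patients with two injections each score 100% or 66.7% depending on which one was missed.

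**Where the cases can occur.** SAP 8.6 presents treatment data on the safety and DLT populations for Phase I, and on the per-protocol and safety populations for Phase IIa. Under SAP 6.1 the per-protocol population needs at least two Pexa-Vec injections, and the DLT population needs all three or a DLT. The one-injection case therefore belongs mainly to the safety population. The two-injection case can also appear in the per-protocol population.

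**Magnesium against the rest of the appendix.** For sodium, potassium, glucose and corrected calcium, the hypo row uses values below the lower limit of normal and the hyper row uses values above the upper limit. Magnesium alone is reversed. Taken literally, 1.5 mmol/L is Grade 3 hypomagnesemia (band >1.23 to 3.30) and 0.35 mmol/L is Grade 3 hypermagnesemia (band <0.4 to 0.3). The grade stays 3 once the labels are exchanged; only the direction changes.

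**The case against.** **Under-dosing is visible elsewhere.** A reader might infer that the RDI rule conceals early discontinuation. The documents do not support that. SAP 8.6.1 also lists and summarises the number of Pexa-Vec administrations, the cumulative dose and the duration of exposure, and adds a table of cancelled, not-done and interrupted administrations with reasons. A patient with one injection shows as one administration of about 10^9 pfu. This objection stands against any claim of concealment. It does not rescue the RDI line, which would contradict those entries.

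**Boosts may not be meant to count.** The schedule row names only the three planned days, and the dose comes from an eCRF page whose handling of boosts cannot be seen. That is fair: the boost figures rest on the literal reading that all actual doses are summed. Nor is 57.1% a constant. It is one boost at the earliest permitted time, and the cases worked here run from 30.8% to 62.5%.

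**Magnesium grading follows the CTCAE itself.** SAP 7.7.2 and 8.8.2 both name CTCAE version 4.03 as the standard, so a careful programmer might override the appendix. A reader should therefore not infer that every low magnesium will be misreported. The error materialises only if the appendix is coded as written. Still, SAP 8.8.2 sends the reader to the appendix for the graded abnormalities, and a specification should not depend on being corrected in programming.

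**Conclusion.** Both points hold as specification errors in descriptive tables. The RDI finding of 100% for one, two or three on-schedule injections is exact, needs only full-volume dosing, and conflicts with the SAP's own definition. The low RDI after boosts is conditional on boosts entering the sum and on their timing. The nivolumab RDI does not share the problem in the same way, because its schedule is open-ended with no fixed number of infusions.

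The magnesium swap is plain from the appendix alone. Both rows read as complete and their neighbours are in order, so a misplaced label in the published copy is unlikely, though a check of the source file would settle it.

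It would be tempting to read either error as touching trial decisions. Neither does. The ORR test and the interim boundaries use response counts, and DLTs are identified through adverse event reporting rather than through these shift tables. The point merits correction before the final tables are run, and no more than that.

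**What to change.** **(a) Dose intensity.** For dose level 1, define Pexa-Vec RDI (%) = 100 x (dose received in the planned D1, D15 and D29 injections / 3 x 10^9 pfu) x 6 / max(6, (last - first planned injection + 14)/7). Checks:

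- one on-time injection: 100 x 1/3 x 6/6 = 33.3%
- two: 100 x 2/3 x 6/6 = 66.7%, whichever later one is missed
- three: 100 x 3/3 x 6/6 = 100%
- third a week late: 100 x 6/7 = 85.7%

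The factor of 6 planned weeks is needed; without it a perfect course would come out as 1/6 = 0.167 per week. For dose level -1, replace 3 x 10^9 by the planned total of the regimen used (three injections of 3 x 10^8 make 9 x 10^8 pfu; if Pexa-Vec stays at 10^9, the total is unchanged). Summarise boosts separately, by number and cumulative dose, and say so in the SAP. One limit: in a course stopped after two injections, a short delay can fall inside the six-week minimum and not show, but the missing third injection does.

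**(b) Magnesium.** Exchange the two sets of limits in Appendix 1.

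The cost is a short SAP edit and two program changes. Data collection and treatment are not affected.
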